8.3 Sample size

The primary endpoint is the 5-year biochemical failure free rate (BFFR) associated with the combined hypofractionated dose regimen and ADT. All patients will be followed for at least 5 years. We expect to observe 5-year BFFR 85% or higher. The annual dropout rate is expected to be at most 1% ~ 2% (or cumulative 5 year dropout rate is less than 10%). If 100 patients will finish 5 year follow up, the width of 95% confidence interval of BFFR will be less than 0.14. To incorporate the dropout rate, the total required sample size will be 110.

8.4 Safety monitoring.

An early stopping boundary will be used to test the hypotheses $H_0: Rt \leq 10\%$ versus $H_1: Rt > 10\%$ where Rt is the rate of grade 3 or greater on either GU or GI toxicity. We derive the one-sided stopping boundary using exact binomial test: at the first stage with 50 patients recruited, if 12 or more patients have experienced grade 3 or greater toxicity with an *attribution* of probably related (see section 10.2), the trial will be stopped. Otherwise, the trial will continue to recruit all 100 patients. If no more than 16 patients out of total 100 patients have experienced grade 3 or greater toxicity as detailed previously, the treatment is considered safe for further investigation. Based on EAST 5 (Copyright © 2009 Cytel Inc) Binomial one-sample exact test for single proportion, this stopping rule gives 87% power to reject unsafe treatment regime if the true toxicity rate is 20%.

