6.0 PATIENT ASSESSMENTS

6.1 Study Parameters

- H&P – at initial consult and following treatment protocol
- PSA – At baseline, 3 and 6 months after treatment, then every 6 months until 3 years, and then annually until year 5
- Testosterone – At baseline, 3 and 6 months after treatment, then every 6 months until 3 years, and then annually until year 5
- Bone Scan - at baseline*
- Pelvic CT or other lymph node assessment - at baseline*
- Symptom assessment (IPSS, SHIM, modified EPIC sheet, as per Appendix I) – At baseline, 3 and 6 months after treatment, then every 6 months until 3 years, and then annually until year 5
- Serum ALT, AST and AP at baseline and one month following initiation of ADT.
- Optional Blood draw collected at baseline and at 3 and 24 months following treatment completion. Patients who have initiated ADT prior to consent for optional blood samples will be ineligible to give extra blood samples.
- Seed placement of at least 3 gold seeds at least 1 week prior to first CT simulation if additional image guidance is not being used
- CT simulation will occur prior to radiation treatment as standard of care and then again during radiation any time after fraction 3 as a QA procedure for monitoring prostate rotation in relation to seed placement. However, second CT simulation after fraction 3 is only necessary if patient had fiducial placement.

* CT/MRI and Bone scan optional except for the patients who are:

1. Gleason 4+3
2. >50% cores positive
3. >1 intermediate risk factor (GS 7, PSA ≥ 10 and T2b-T2c).

Safety run-in phase

A phase I trial of SBRT in prostate cancer (n=45) composed of 60% intermediate-risk, localized patients where 22% of men were treated with androgen deprivation has been recently reported (ref. 7). This trial used considerably higher SBRT doses than our current trial (9-10 Gy x5 versus 7.25 Gy x5) and still reported no Grade 3 or 4 GI or GU acute toxicities (<90 days). Therefore, we believe our more modest SBRT fractionation scheme of 7.25 Gy x5 is likely safe in combination with androgen deprivation. To ensure that this combination is safe, the first six patients will be treated and analyzed for toxicity for 3

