months after radiation. Six patients will be enrolled at the proposed dose of SBRT and androgen deprivation therapy and if 0 or 1 patient experiences a dose limiting toxicity (DLT) then this regimen will be considered safe (note: accrual will continue while the interim analysis is being conducted). If >1 patient experiences a DLT than this regimen will be considered unsafe and the trial will stop at this point. DLT for the purpose of calculation of the maximum tolerated dose (MTD) includes medically unmanageable Grade 3 or any Grade 4 toxicity with an *attribution* of probably related to protocol intervention (see section 10.2).

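### Section 8.4 states 87% power for its toxicity rule, but the rule as written has 81.0%; it also judges 100 patients where 8.3 enrols 110, and gives no follow-up for the 50-patient look.

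*Combined protocol and SAP*

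**What the plan says.** Section 8.4 tests whether the rate of grade 3 or higher GU or GI toxicity exceeds 10%, with a one-sided exact binomial rule in two stages. Counted events are those attributed as probably related.

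- Stage 1: "at the first stage with 50 patients recruited, if 12 or more patients have experienced grade 3 or greater toxicity", the trial stops.
- Continuation: "Otherwise, the trial will continue to recruit all 100 patients".
- Final judgement: the condition for calling the regimen safe is "If no more than 16 patients out of total 100 patients have experienced grade 3 or greater toxicity as detailed previously". Unsafe therefore means 17 or more.
- Stated property: "this stopping rule gives 87% power to reject unsafe treatment regime if the true toxicity rate is 20" per cent.

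No type I error is stated, and neither stage has a toxicity window or minimum follow-up.

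Section 8.3, immediately before, sizes the trial on 100 patients finishing 5 years and then adds: "To incorporate the dropout rate, the total required sample size will be 110".

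The six-patient run-in described in Section 6.1 does have a window: "the first six patients will be treated and analyzed for toxicity for 3" months after radiation. There the plan also notes that "accrual will continue while the interim analysis is being conducted". Sections 5.0 and 5.5 put at least one month of ADT before radiation, and radiation itself takes two weeks.

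**The concern.** The power figure is the plan's only statement of how well the rule detects an unsafe regimen. If the figure and the boundary do not belong together, a reader cannot tell which was intended, and the chance of missing a 20% toxicity rate is 19% rather than the 13% that the plan implies.

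The 100 and 110 matter because a count boundary has meaning only with its denominator. Ten enrolled patients have no stated place in the final safety judgement.

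The timing matters because an exact binomial boundary of 12 in 50 presumes 50 observed outcomes. A patient recruited last month may still be in the ADT lead-in and cannot yet have radiation toxicity.

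**Working it through.** **1. Power of the rule as written**

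Inputs, all from 8.4: n1 = 50 with stop at 12 or more; n = 100 with unsafe at r = 17 or more; rates 10% (null) and 20% (alternative).

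Formula, with X1 and X2 independent Binomial(50, p):

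P(reject) = P(X1 ≥ 12) + Σ(x = 0 to 11) P(X1 = x) · P(X2 ≥ r − x)

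For r = 17:
- p = 0.20: 0.2893 + 0.5207 = 0.8101
- p = 0.10: 0.0032 + 0.0185 = 0.0218

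The stated 87% is not reproduced. The nearest variants, all keeping 12 of 50 at stage 1, are:

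| Final boundary | Power at 20% | Type I error at 10% |
|---|---|---|
| ≥17 of 100 (as written) | 81.0% | 2.2% |
| ≥16 of 100 | 87.2% | 4.05% |
| ≥18 of 110 | 86.1% | 2.6% |

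Moving the final cut-off by one patient, so that 16 counts as unsafe, reproduces 87% with the plan's own 100. The 110-patient variant comes within a point but matches neither the 16 nor the 100 in the text.

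The stage 1 look contributes almost nothing to overall power. A single test at ≥17 of 100 has 80.8%, against 81.0% with the look.

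**2. Denominator**

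In 8.3, 100 is the number finishing five years and 110 the number enrolled. In 8.4, 100 is the number recruited and the number judged. Both cannot be the enrolment total.

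**3. Timing of the stage 1 look, if it is done at the 50th enrolment**

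Inputs:
- Accrual of 7 per month (Section 9.0), or 110/26 ≈ 4.2 per month, implied by 110 patients between June 2013 and August 2015. Uniform accrual is my assumption.
- Lag from enrolment to end of radiation of 1.5 months (one month of ADT plus two weeks), with an assumed range of 0.5 to 2.5. The short end allows for ADT begun before enrolment.

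Patients with radiation finished = 50 − rate × lag:
- 7 per month: 50 − 10.5 = 39.5, taken as 39
- 4.2 per month: 50 − 6.3 = 43.7, taken as 44
- Over the lag range: about 32 to 46 at 7 per month, and 39 to 48 at 4.2 per month

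Chance of reaching 12 events at a true 20% rate, counting every irradiated patient as fully observed (which favours the plan):

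| Outcomes observed | P(X ≥ 12) |
|---|---|
| 50 | 28.9% |
| 48 | 24.1% |
| 44 | 15.4% |
| 39 | 7.4% |
| 32 | 1.7% |

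The direction is the same throughout; the size depends on the assumptions.

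**The case against.** On the power figure there is little to say in defence. No type I error is stated, so the intended boundary cannot be recovered, and both candidates on 100 patients stay below 5%. That is a reason to ask which was meant; it does not show that the text is consistent.

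On the denominator, 100 evaluable patients out of 110 enrolled is a plausible intent, since 8.3 uses the two numbers that way. But 8.4 speaks of recruiting 100, so the passages still conflict. A reader might infer that type I error really rises to 4.7%, which is what 17 events in 110 fully observed patients would give. No section proposes that rule, and 8.3 itself allows for nearly 10% dropout, so the inference is not supported.

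On timing, the strongest reply is that the wording about 50 recruited patients may only name the stage size. This stands. The text does not establish that the look lacks 50 outcomes, only that its timing and follow-up are unspecified. The 7-per-month rate is also an all-site average: Section 9.0 opens two sites 11 months after the first, and 7 per month would fill 110 places in about 16 months rather than 26. The lowest stopping probabilities therefore deserve the least weight.

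Other oversight continues as well: adverse events are recorded throughout, cross-site calls are held semimonthly, and a safety committee reviews annually. None of these has a numeric boundary. After the run-in, the stage 1 look is the only early stop that does.

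**Conclusion.** The power statement in 8.4 is wrong for the rule in 8.4: 81.0%, not 87%, with type I error 2.2%. This is exact and needs no assumption beyond the binomial model that the plan itself uses. The discrepancy is one patient at the final boundary. The documents do not show whether the boundary or the power figure is the slip.

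The 100 and 110 contradict each other and leave the final denominator undefined.

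The timing point is secondary and conditional. If the look takes place at the 50th enrolment, its chance of stopping at a 20% rate falls below 28.9%, to roughly 15% or 7% under the central assumptions. It would be wrong to infer that the safety rule as a whole loses power, because the final analysis carries nearly all of it (81.0% with the look, 80.8% without). What is lost is early protection of patients.

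**What to change.** In 8.4:

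1. Reconcile the final boundary with the stated power, and restate power and type I error for the boundary kept, using the first table above.
2. Reconcile 100 with 110. State who is in the final denominator and the follow-up each patient needs in order to count.
3. Define stage 1 on the first 50 treated patients with a stated minimum follow-up; the run-in's 3-month post-radiation assessment is one window the plan already uses. State whether events after that window, in patients treated earlier, count toward the 12, because the chance of stopping depends on it.

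Items 1 and 2 cost only wording. Item 3 delays completion of the look by about 3.5 to 5.5 months (lag of 0.5 to 2.5 months plus 3). If accrual continues meanwhile, enrolment would by then be 50 + 4.2 × (3.5 to 5.5), about 65 to 73, or 50 + 7 × (3.5 to 5.5), about 75 to 89. A 3-month window also says little about late toxicity, which would rest mainly on the final assessment.

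The document carries a December 2021 date and projected accrual to close in August 2015. If accrual has closed, item 3 becomes a reporting matter: say when the look was done and with what follow-up, and correct the denominator and the power statement.

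### Section 8.4 sets no numeric accrual stop before patient 50 or between patients 50 and 100, so enrolment could continue after its own safe conclusion is out of reach

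*Combined protocol and SAP*

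**What the plan says.** Section 8.4 (Safety monitoring) tests a null toxicity rate of at most 10%, where the rate "is the rate of grade 3 or greater on either GU or GI toxicity". The method is given as "We derive the one-sided stopping boundary using exact binomial test". Three instructions follow.

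- Stage 1: "at the first stage with 50 patients recruited, if 12 or more patients have experienced grade 3 or greater toxicity", with attribution probably related, the trial stops.
- Between the looks: "Otherwise, the trial will continue to recruit all 100 patients".
- Final: "If no more than 16 patients out of total 100 patients have experienced grade 3 or greater toxicity as detailed previously", the regimen passes.

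The section adds that "this stopping rule gives 87% power to reject unsafe treatment regime if the true toxicity rate is 20"%. It states no type I error and no time window for counting events.

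Elsewhere, the safety run-in in section 6.1 has a numeric rule, but only for the first six patients. Section 16.0 (Quality Assurance) provides semimonthly cross-site teleconferences that review adverse events, attended by an internal physician monitor. Section 18.0 gives the principal investigator the task of checking that safety supports continuing, with annual committee review. Neither section sets a number. Section 8.3 plans 110 patients; section 8.4 works with 100.

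**The concern.** The number of patients with a qualifying event cannot fall, provided attributions are not later downgraded. Once a 12th such patient is identified before the 50th recruit, the stage-1 stop is certain. Once a 17th is identified before the 100th recruit, the final criterion can no longer be met. The rule acts at neither moment, and its wording after stage 1 points towards full recruitment.

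At stake is the exposure of further patients to a regimen that can no longer pass the plan's own toxicity criterion, when their enrolment cannot alter that toxicity verdict.

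**Working it through.** **1. The plan's own figure.** Inputs from 8.4: 50 patients per stage, stage-1 stop at 12 or more, final failure at r or more, where r = 17 as written.

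P(reject) = P(X50 ≥ 12) + Σ(x = 0 to 11) P(X50 = x) · P(Y50 ≥ r − x), with X50 and Y50 independent binomial(50, p).

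| Final cut-off | p = 10% | p = 20% |
|---|---|---|
| r = 17 (as written) | 2.2% | 28.9% + 52.1% = 81.0% |
| r = 16 | 4.05% | 87.2% |

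The stated 87% is not reproduced by the written limit. It fits a limit one patient lower. With the final sample raised to 110 and r = 17, the power is 90.9%.

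**2. How early the verdict can be settled (r = 17).** With 11 events at patient 50 the trial continues. Six more events can bring the 17th at patient 50 + 6 = 56, leaving 44 to reach 100 or 54 to reach 110. If events are known at once and p = 20%:

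- The chance of a 12th event by patient 49 is 26.5%.
- The chance of passing stage 1 and then reaching the 17th event before patient 100 is 50.8%. This is 50.8 / 71.1, or about 71%, of trials that pass stage 1.
- When the 17th falls in patients 51-100, its mean position is patient 84, so about 16 more are enrolled to reach 100.

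**3. Enrolment saved if events are known at once.** Under the written rule, expected enrolment is 50 + 50 · P(X50 ≤ 11). The curtailed rule stops at the 12th event within the first 50 or at the 17th overall, evaluated by an exact patient-by-patient recursion.

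| True rate | Written | Curtailed | Spared per trial that fails |
|---|---|---|---|
| 20% | 85.5 | 75.3 | 12.6 |
| 30% | 57.0 | 42.3 | 14.7 |
| 40% | 50.3 | 30.1 | 20.2 |

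Simulation with 200,000 trials per rate agrees to within 0.1 (85.6 to 75.4 at 20%; 57.0 to 42.4 at 30%).

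**4. Delayed onset.** The documents give no onset distribution. Assumed: radiation complete 1.5 months after enrolment, and onset uniform over the window shown. The rate of 7 per month is from section 9.0. The rate of 4 per month is what that section's dates imply: June 2013 to August 2015 is about 26 months, and 110 / 26 ≈ 4.2. Mean patients spared:

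| Accrual | Onset window | 20% | 30% | 40% |
|---|---|---|---|---|
| 7 per month | 0-6 months | about 2 | 13 | 25 |
| 7 per month | 0-12 months | about 0 | 1.5 | 7 |
| 4 per month | 0-6 months | about 6 | 19 | 16 |
| 4 per month | 0-12 months | about 2 | 14 | 25 |

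**5. Effect on the verdict.** If the 12th event is identified by the 50th recruit, the written rule stops the trial anyway. If the 17th is identified at any later point in accrual to 100, the final count is at least 17 anyway. The same outcomes therefore give the same verdicts, and 2.2% and 81.0% are unchanged. This needs the time limit on the 12-event stop. Suppose the 12th event among the first 50 surfaces when 75 are enrolled. The written rule has then passed stage 1 and could still finish at 16 or fewer, whereas a stop without a time limit would end the trial.

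**6. Effect on the primary estimate.** The width of the 95% interval at a biochemical failure-free rate of 85% is 2 × 1.96 × √(0.85 × 0.15 / n). For n = 100 this is 0.140, which matches section 8.3. For n = 70 it is 0.167, before dropout.

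**The case against.** A two-look exact design without curtailment is a standard choice, not a calculation error. That stands.

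A reader might infer that sites are obliged to enrol to 100 under a regimen already declared unsafe. The documents do not support that. Nothing in 8.4 forbids an earlier halt, and the oversight in sections 16.0 and 18.0 could impose one. Section 8.4 orders a stop only at stage 1. Its final limit is an end-of-trial judgement that defines when the regimen passes, and failure at 17 is implied by the power statement. What is missing is a number that requires action.

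A reader might also infer that the extra patients contribute nothing. That is true of the toxicity verdict only, because they still add precision to the 5-year biochemical failure-free rate.

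The benefit is also small in some settings. At 20%, the only alternative that 8.4 names, delayed onset at 7 per month cuts the saving to about 1.6 patients (0-6 months) or about 0.05 (0-12 months). The larger figures need rates of 30-40%, whereas section 1.0 cites grade 3 or higher rectal toxicity in 2 of 32 patients in one study and at most 2% GI and 4% GU in another. For slow-onset toxicity, the larger weakness is that both looks are tied to recruitment counts with no follow-up window. All of this limits the size of the point, but does not supply the missing trigger.

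**Conclusion.** The point holds as a cheap improvement. Section 8.4 has no numeric trigger before the 50th recruit or between the 50th and the 100th, so the trial could keep enrolling after its own criterion can no longer return a safe conclusion. No other numeric rule covers that interval.

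The size rests on how quickly events become known. About 10 patients are saved on average at a 20% rate if events are known at once, and close to none at 7 per month with onset over a year. The saving is larger at 30-40% or with slower accrual. The onset windows are assumptions. The figures use the written 17-event limit and 100 patients, both of which need reconciling within the documents.

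The reading that enrolment past this point is compulsory goes further than the text. If accrual has already closed, as the planned August 2015 date suggests, the change matters only for later use of the rule.

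**What to change.** First, reconcile the final limit with the stated power (17 or more gives 81.0%; 16 or more gives 87.2%), and the 100 patients in 8.4 with the 110 in 8.3. State which patients the final count covers.

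Then replace the sentence that directs recruitment to 100 with text to this effect: accrual stops as soon as the 12th qualifying patient is identified at or before the 50th recruit, or as soon as the number of qualifying patients exceeds the final limit (the 17th as written) at any time during accrual; otherwise recruitment continues to the planned total.

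The cost is a sentence or two and a running tally. Section 10.3.1 already puts all adverse events on case report forms, and the semimonthly teleconferences already review them. With the time limit on the 12-event stop, the toxicity verdict and its error rates do not change. The real price is that after an early stop both the toxicity and the 5-year biochemical failure-free estimates rest on fewer patients, and the plan should say so.

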8.0 DATA ANALYSIS AND SPECIAL CONSIDERATIONS

8.1 Primary Analysis:

The primary objective is to estimate the 5-year biochemical failure free rate (BFFR) associated with the combined hypofractionated dose regimen and ADT. The BFFR is defined as a binary indicator whether PSA has increased by 2 ng/ml or more above the nadir PSA any time before the end of 5 years. The primary analysis will be performed by first obtaining the Kaplan-Meier (K-M) estimate of the biochemical failure free survival, and then estimating the 5-year biochemical failure free rate (BFFR) from this K-M curve together with 95% confidence interval. Greenwood formula will be used to calculate the variance of K-M estimate.

8.2 Secondary objectives:

8.2.1. Assess the incidence of grade 3 or greater late GU and GI toxicity and self-reported quality of life data.

Kaplan-Meier estimate of the incidence of grade 3 or greater late GU and GI toxicity will be constructed together with 95% confidence interval. Patient reported quality of life will be summarized using means and standard deviation for continuous measures, the contingency tables for categorical measures.

8.2.2 Assess clinical and pathologic control rates associated with the combined hypofractionated dose regimen and ADT.

Assessments will be performed 3 and 6 months after treatment and then every 6 months until 3 years, then annually until year 5. These rates will be estimated from Kaplan-Meier curves together with 95% confidence intervals.

Disease-Free Survival, measured from the date of enrollment to the date of documented progression or date of death using Kaplan-Meier estimates. Progression will be documented by PSA, bone scan, or biopsies.

Time to Local Progression (TLP) will be measured from the date of enrollment to the date of documented local progression using Kaplan-Meier estimates. Patients with new palpable abnormality on digital rectal examination or PSA failure at any point in time will also be offered biopsy to distinguish between local and distant failures. Patients who do not undergo biopsy will be censored at the last point of time they were considered locally controlled by digital rectal examination and PSA and considered not evaluable for further assessment.

Time to Distant Failure (TDF) will be measured from the date of enrollment to the date of documented metastatic disease. Patients who have negative biopsy following PSA failure or palpable abnormality will be considered to have only distant failure.

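### The Section 8.4 safety rule as written has 81% power at a 20% toxicity rate, not the stated 87%; cutoff and power need to be reconciled

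*Combined protocol and SAP*

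**What the plan says.** Section 8.4 of the combined protocol and SAP tests a null toxicity rate of at most 10% against a higher rate, one-sided, "where Rt is the rate of grade 3 or greater on either GU or GI toxicity". The rule has two stages.

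- **First stage:** "at the first stage with 50 patients recruited, if 12 or more patients have experienced grade 3 or greater toxicity", recruitment ends. Only events judged probably related to treatment count towards this limit.
- **Second stage:** "Otherwise, the trial will continue to recruit all 100 patients". The final criterion then reads "If no more than 16 patients out of total 100 patients have experienced grade 3 or greater toxicity", in which case the regimen is accepted as safe for further study.

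The section names an exact one-sample binomial test in a commercial design package as its basis and claims that "this stopping rule gives 87% power to reject unsafe treatment regime if the true toxicity rate is 20" per cent. It does not state a type I error. The cutoffs and the power claim stand in the same paragraph, and no other section restates or corrects them.

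**The concern.** The two cutoffs and the two sample sizes define the rule completely, so its power at 20% is a fixed number that can be computed without knowing the intended alpha. Sixteen events in 100 counts as safe, so rejection begins at 17. A rejection limit of 17 looked too high for 87% power when 20 events are expected.

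Section 8.4 holds the plan's only numerical criterion for declaring the regimen safe for further investigation. If the power is overstated, anyone relying on it (IRB, safety committee, later readers) believes the rule protects better against a 20% toxicity rate than it does. If the cutoff was mistranscribed, a result of exactly 16 in 100 would be labelled safe although the design as computed would have rejected it.

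**Working it through.** **Inputs, all from Section 8.4:** first-stage size 50 with stopping at X1 ≥ 12; total size 100; safe at a total of 16 or fewer, so rejection at r = 17; null rate 0.10; alternative rate 0.20; stated power 87%.

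**Formula.** With X1 and X2 independent binomial counts in 50 patients each at rate p,

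power(p) = P(X1 ≥ 12) + Σ (x = 0 to 11) P(X1 = x) · P(X2 ≥ r − x).

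**Rule as written, r = 17, p = 0.20.**
- Early stop: P(X1 ≥ 12) = 0.28933.
- Rejection at the end: 0.52074.
- Power: 0.28933 + 0.52074 = 0.81007, or 81.0%.
- Chance of a safe label: 1 − 0.810 = 0.190. The stated power implies 1 − 0.87 = 0.13.

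**Rule as written, p = 0.10.** Type I error 0.0218, of which 0.0032 comes from the early stop.

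The stated 87% is not reproduced; the gap is 87 − 81 = 6 percentage points.

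**Which final cutoff gives 87%?** With the first stage at 12 of 50 and 100 patients in total:

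| Reject at | Power at 20% | Type I error at 10% |
|---|---|---|
| 15 or more | 92.0% | 7.3% |
| 16 or more | 87.2% | 4.1% |
| 17 or more (as written) | 81.0% | 2.2% |
| 18 or more | 73.5% | 1.2% |

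Only rejection at 16 or more matches, and its type I error also falls just under 5%.

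**Could something else explain 87% while keeping rejection at 17?**
- No interim look: 80.8%.
- First-stage cutoff of 10, 11, 13 or 14: 83.1%, 81.6%, 80.8%, 80.8%. A cutoff of 9 gives 85.7%, still below 87%, with a type I error of 6.6%.
- All 110 patients of Section 8.3 counted: 90.9%, type I error 4.7%.
- Normal approximation to 17 or more of 100, with continuity correction: 80.9%.

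**How far apart are the two candidate rules?** They differ only when there is no early stop and the total is exactly 16. That has probability 0.8722 − 0.8101 = 0.0621 at a 20% rate and 0.0405 − 0.0218 ≈ 0.019 at 10%. The written rule reaches 87% power only at a true rate of about 21.0%.

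**The case against.** The arithmetic is not in dispute. The objections concern the explanation and the weight.

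**Other sources of the 87%.** Keeping both written cutoffs and letting the total vary, 105 patients give 86.6% and 106 give 87.6%. Since Section 8.3 inflates for dropout ("To incorporate the dropout rate, the total required sample size will be 110") and Section 9.0 assumes 5% dropout, a software run with more than 100 patients is conceivable. This stands as a reason not to treat the off-by-one as established. It does not rescue the figure: neither 105 nor 106 appears in the documents, and Section 8.4 says 100.

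**The 19% is not the whole trial's error.** The six-patient safety run-in in Section 6.1 also stops the trial if more than one patient has a dose-limiting toxicity. In the extreme case where every counted event is such a toxicity within three months and those six are among the first 50, the chance of a safe label at 20% falls to 15.1%. This is fair: 19% describes the Section 8.4 rule alone and is an upper bound for the trial.

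**The early-stop probability is nominal.** The look is triggered by recruitment of 50 patients and no toxicity window is given, so some outcomes may be incomplete. This also stands, but the stated 87% presumably rests on the same simplification, and removing the look altogether changes the power only to 80.8%.

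**Consequences are small and late.** The written cutoff is clear and can be applied, and the two candidates differ on one outcome. The projected close of accrual was August 2015, while the document is dated December 2021. Late toxicity is also reported separately under Section 8.2.1 ("Kaplan-Meier estimate of the incidence of grade 3 or greater late GU and GI toxicity will be constructed"). All this limits the reach of the error, but the stated power remains wrong for the stated rule.

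**Conclusion.** The concern holds. The rule in Section 8.4 has exact power of 81.0% at a 20% toxicity rate and a type I error of 2.2% at 10%; the stated 87% is 6 points too high. With the documented design of 50 then 100 patients and the 12-of-50 stop, 87% corresponds to rejection at 16 or more. That pattern suggests a rejection limit of 16 written down as an acceptance limit, but the software output is not in the documents and the cause cannot be confirmed.

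The calculation assumes 100 evaluable patients with complete outcomes and a common, independent toxicity probability, as the plan's own binomial test does. The rate in question is that of events that count under Section 8.4, including its attribution condition.

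The effect is confined to the final safe-for-further-investigation label. The 12-of-50 stop, the run-in, the Kaplan-Meier toxicity estimate, the primary endpoint and the sample size are unaffected. The point should be fixed because a safety criterion carries an operating characteristic that it does not have.

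**What to change.** Check the original software output and make the final cutoff and the power statement in Section 8.4 agree.

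- If the written cutoff is the designed one, restate the power as 81% and give the type I error as 2.2%.
- If the output shows a different boundary, align the text with it and report that boundary's power and type I error.

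Which cutoff applies is for the sponsor to decide, on the output and not on the observed count. In either case, state the type I error. It would also help to say which 100 of the 110 patients planned in Section 8.3 enter the final count, although the discrepancy does not depend on that.

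The cost is one look-up and one or two sentences. No patients are added, and the interim stop, the primary endpoint and the sample size stay as they are.
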